4.4.1 Clinical Criteria for Early Study Termination

There are no prespecified criteria for terminating the study early.

A primary objective of this early Phase 1 study is to identify the maximum safe and well-tolerated dose and/or dosing regimen that achieve PK, pharmacodynamic, and/or biologic targets in humans based on preclinical or early clinical data. Therefore, it is possible that study participants may not receive all doses specified in the protocol if this objective is achieved at lesser dose levels in this study. This would not be defined as early termination of the study, but rather an earlier than anticipated achievement of the study objective(s). If a finding (eg, PK, pharmacodynamic, efficacy, biologic targets, etc.) from another preclinical or clinical study using the study intervention(s), comparator(s), drug(s) of the same class, or methodology(ies) used in this study results in the study(ies) or program being stopped for nonsafety reasons, this also does not meet the definition of early study termination.

Early study termination is defined as a permanent discontinuation of the study due to unanticipated concerns of safety to the study participants arising from clinical or preclinical studies with the study intervention(s), comparator(s), drug(s) of the same class, or methodology(ies) used in this study.

8. [REDACTED]

Demographics

10. Is from 18 years to 60 years of age inclusive, at the time of signing the informed consent.

11. Has a Body Mass Index (BMI) ≤ 35 kg/m². BMI = weight (kg)/height (m)².

12. May be either male or female, satisfying the sex-specific requirements specified below:

Male Participants

Contraceptive use by men should be consistent with local regulations regarding the methods of contraception for those participating in clinical studies.

Male participants are eligible to participate if they agree to the following during the intervention period and for at least 35 days after the last dose of study medication, corresponding to the time needed to eliminate the study medication (i.e., 5 terminal half-lives):

- a. To be abstinent from heterosexual intercourse as their preferred and usual lifestyle (abstinent on a long term and persistent basis) and to remain abstinent.

OR

- b. To use contraception unless confirmed to be azoospermic (vasectomized or secondary to medical cause [Appendix 5: Contraceptive Guidance and Pregnancy Testing]) as detailed below:
 - To use a male condom, and for the partner to use an additional contraceptive method when having penile-vaginal intercourse with a WOCBP who is not currently pregnant.

Note: Men with a pregnant or breastfeeding partner must agree to remain abstinent from penile-vaginal intercourse or use a male condom during each episode of penile-vaginal penetration.

Female Participants

- A female participant is eligible to participate if she is not pregnant or breastfeeding AND one of the following conditions applies:
 - She is a woman of nonchildbearing potential (WONCBP), as defined in Appendix [5]
OR
 - She is a woman of childbearing potential (WOCBP) and using a contraceptive method that is highly effective (with a failure rate of <1% per year), with low user dependency, or is abstinent from heterosexual intercourse as her preferred and usual lifestyle (abstinent on a long term and persistent basis), as described in Appendix [5] during the intervention period and for at least 35 days after the last dose of study medication, [REDACTED]
[REDACTED] The investigator should evaluate the potential for contraceptive method failure (e.g., noncompliance, recently initiated) in relation to the first dose of study intervention.
 - A WOCBP must have a negative highly sensitive pregnancy test (urine or serum, as required by local regulations) within 24 hours before the first dose of study medication.
 - If a urine test cannot be confirmed as negative (e.g., an ambiguous result), a serum pregnancy test is required. In such cases, the participant must be excluded from participation if the serum pregnancy result is positive.
 - -Additional requirements for pregnancy testing during and after study intervention are located in Appendix [2].
 - -The investigator is responsible for review of medical history, menstrual history, and recent sexual activity to decrease the risk for inclusion of a woman with an early undetected pregnancy.

Informed Consent

13. The participant provides written informed consent/assent for the study. The participant may also provide consent/assent for future biomedical research. However, the participant may participate in the main study without participating in future biomedical research.

5.2 Exclusion Criteria

The participant must be excluded from the study if the participant:

Medical Conditions

1. Has acute (primary) HIV-1 infection.
2. Has a history of clinically significant endocrine, gastrointestinal, cardiovascular, hematological, hepatic (with the exception of Gilbert's disease), immunological (outside of HIV-1 infection), renal, respiratory, genitourinary, or major neurological (including stroke and chronic seizures) abnormalities or diseases. Participants with a remote history of uncomplicated medical events (e.g., uncomplicated kidney stones, as defined as spontaneous passage and no recurrence in the last 5 years, or childhood asthma) may be enrolled in the study at the discretion of the investigator.
3. Is mentally or legally incapacitated at the time of pre-study (screening) visit or expected during the conduct of the study or has a history of a clinically significant psychiatric disorder of the last 5 years. Participants who have had situational depression may be enrolled in the study at the discretion of the investigator.
4. Has a history of cancer (malignancy).

Exceptions: Participants with adequately treated disease deemed "cured," who, in the opinion of the trial investigator, are highly unlikely to sustain a recurrence for the duration of the trial may be enrolled at the discretion of the investigator.

5. Participant has an estimated creatinine clearance (CrCl) ≤ 90 mL/min based on the Cockcroft-Gault (CG) Equation.

Cockcroft-Gault Equation:

$$\text{ClCr} = \frac{(140 - \text{age}[\text{yr}])(\text{body wt}[\text{kg}])}{(72)(\text{serum creat}[\text{mg/dL}])}$$

[When creatinine is measured in micromole/litre, use this formula]

$$\text{ClCr} = \frac{(140 - \text{age}[\text{yr}])(\text{body wt}[\text{kg}])}{(72)(\text{serum creatinine}[\text{micromol/L}] \times 0.0113)}$$

For females, multiple the result by 0.85.

At the discretion of the investigator, a measured creatinine clearance, as determined by a 24-hour urine collection, may be used in place of, or in conjunction with, the estimate of the creatinine clearance.

Participants who have a measured creatinine clearance of up to 10% below 90 mL/min may be enrolled in the study at the discretion of the investigator.

6. Has a history of significant multiple and/or severe allergies (e.g., food, drug, latex allergy), or has had an anaphylactic reaction or significant intolerability (i.e., systemic allergic reaction) to prescription or non-prescription drugs or food; or has hereditary galactose intolerance, lactase deficiency, or glucose-galactose malabsorption.
7. Is positive for hepatitis B surface antigen.
8. Has a history of chronic hepatitis C unless there has been documented cure and/or participant with a positive serologic test for Hepatitis C Virus (HCV) has a negative HCV VL.
9. Had major surgery, donated or lost 1 unit of blood (approximately 500 mL) within 4 weeks prior to the pre-study (screening) visit.

Prior/Concomitant Therapy

10. Is unable to refrain from or anticipates the use of any medication, including prescription and nonprescription drugs or herbal remedies beginning approximately 2 weeks (or 5 half-lives) prior to administration of the initial dose of study drug, throughout the study, until the post-study visit. There may be certain medications that are permitted (see Section 6.5).

Prior/Concurrent Clinical Study Experience

11. Has participated in another investigational study within 4 weeks (or 5 half-lives, whichever is greater) prior to the pre-study (screening) visit. The window will be derived from the date of the last visit in the previous study.

Diagnostic Assessments

12. Has a clinically significant abnormality on the ECG performed at the pre-study (screening) visit and/or prior to administration of the initial dose of study drug.

Other Exclusions

13. Is unwilling to comply with the study restrictions (see Section 5.3 for a complete summary of study restrictions).
14. Is under the age of legal consent or not capable of giving consent.
15. Has been committed to an institution by way of official or judicial order.
16. Is an excessive smoker (i.e., more than 10 cigarettes/day) and is unwilling to restrict smoking to ≤ 10 cigarettes per day.

17. Consumes more than 3 glasses of alcoholic beverages (1 glass is approximately equivalent to: beer [354 mL/12 ounces], wine [118 mL/4 ounces], or distilled spirits [29.5 mL/1 ounce]) per day. Participants who consume 4 glasses of alcoholic beverages per day may be enrolled at the discretion of the investigator.
18. Consumes excessive amounts, defined as more than 6 servings (1 serving is approximately equivalent to 120 mg of caffeine) of coffee, tea, cola, energy drinks, or other caffeinated beverages per day.
19. Has a positive urine drug screen (except for cannabis) at screening and/or pre-dose; rechecks are allowed.
20. Presents any concern to the investigator regarding safe participation in the study or for any other reason the investigator considers the participant inappropriate for participation in the study.
21. Is or has an immediate family member (eg, spouse, parent/legal guardian, sibling, or child) who is investigational site or Sponsor staff directly involved with this study.

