Blood for Genetic Analysis ^s		X																				

All Panels (Panels A-D) ^a																						
Study Period	Screening ^b	Intervention																Post-study ^c				
Scheduled Hour		Pre-dose	0	0.5	1	1.5	2	3	4	5	6	8	12	24	48	72	120	168	240	336	504	

a. Panels A-D will be conducted sequentially. Panels B-D will proceed after review of data from prior panel.
 
b. Participants will be screened within approx. 4 weeks prior to administration of study drug.
 
c. The post-study visit will occur approximately 35 days following administration of the study drug. Follow up for any clinical or laboratory adverse experiences should occur by phone or in person if the post-study visit occurs prior to 35 days following the dose of study drug.
 
d. Substances include: Drugs, alcohol, tobacco, and caffeine.
 
e. Participants will be admitted to the CRU the evening before scheduled dosing.
 
f. Standard meals will be given approx. 4 (lunch) and 10 (dinner) hrs post-dose. Snacks will be offered at approximately 8 and 13 hrs post-dose. See Section 5.3.1.
 
g. A standard breakfast is to be administered approx. 30 minutes prior to dosing in Panel D only. The fat content of this breakfast (i.e., high, moderate, or low) will be determined following the review of emerging safety and PK data from the ongoing studies, Protocols 001 and 002.
 
h. Pre-dose physical exam, urine drug screen and laboratory assessments may be conducted within 24 hrs prior to dosing.
 
i. Participants should be resting in the semi-recumbent position for at least 10 minutes prior to obtaining HR and BP.
 
j. Following measurement of the semi-recumbent HR and BP, participants assume a standing position for approximately 2 minutes and then orthostatic HR and BP will be obtained.
 
k. ECGs are performed after the participant has remained in a semi-recumbent position for at least 10 minutes.
 
l. Pre-dose ECGs and VS (HR and BP) will be obtained in triplicate at least 1-2 minutes apart within 3 hrs prior to dosing.
 
m. For post-menopausal females only.
 
n. Drug screen at screening and pre-dose are mandatory; any additional drug screens are conducted per site SOP and/or at the investigator's discretion.
 
o. Safety laboratory samples (hematology, urinalysis, and chemistry) will be collected after at least an 8-hr fast. Screening hematology labs will include PT/INR measurements.
 
p. Serum/urine (as required by local regulations) β-human chorionic gonadotrophin (β-hCG) to be performed in women of childbearing potential (WOCBP) only.
 
q. Leftover plasma samples will be stored for future biomedical research if the participant signs the Future Biomedical Research consent.
 
r. For participants who initiate follow-on anti-retroviral therapy (ART), blood for HIV-1 viral RNA and viral resistance will be collected at timepoints up to the initiation of ART. At the timepoint immediately prior to initiation of ART an additional blood sample collected for viral resistance testing may be taken for extraction of proviral DNA. This proviral DNA will be frozen and analyzed for the presence of viral resistance mutations only if standard Sanger sequencing cannot be performed because plasma viral load is too low at this time point. In addition, ultra-deep sequencing may be performed on this proviral DNA sample in the event that further information on viral resistance is required.
 
s. This sample should be drawn for planned analysis of the association between genetic variants in DNA and drug response. This sample will not be collected at that site if there is either a local law or regulation prohibiting collection, or if the IRB/IEC does not approve the collection of the sample for these purposes. If the sample is collected, leftover extracted DNA will be stored for future biomedical research if the participant signs the future biomedical research consent. If the planned genetic analyses are not approved, but future biomedical research is approved and consent is given, this sample will be collected for the purpose of future biomedical research.
																						

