6.5 Concomitant Therapy

If a participant does not discontinue all prior medications within 14 days or 5 half-lives of the first dose of study intervention, he/she may be included in the study if the investigator can rationalize that the specific use of a prior medication is not clinically relevant within the context of the study.

Concurrent use of any prescription or nonprescription medication, or concurrent vaccination, during the ongoing study (i.e., after randomization or intervention allocation) must first be discussed between the investigator and Sponsor prior to administration, unless appropriate medical care necessitates that therapy or vaccination should begin before the investigator and

Sponsor can consult. The participant will be allowed to continue in the study if both the Sponsor and the investigator agree.

Paracetamol/acetaminophen (maximum 4 grams in 24 hours) or ibuprofen (maximum 600 mg in 24 hours) may be used for minor ailments without prior consultation with the Sponsor.

[REDACTED]

[REDACTED]

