8 STUDY ASSESSMENTS AND PROCEDURES

- Study procedures and their timing are summarized in the SoA.
- Adherence to the study design requirements, including those specified in the SoA, is essential and required for study conduct.

- The investigator is responsible for ensuring that procedures are conducted by appropriately qualified (by education, training, and experience) staff. Delegation of study site personnel responsibilities will be documented in the Investigator Trial File Binder (or equivalent).
- All study-related medical (or dental) decisions must be made by an investigator who is a qualified physician (or dentist when appropriate).
- All screening evaluations must be completed and reviewed to confirm that potential participants meet all eligibility criteria. The investigator will maintain a screening log to record details of all participants screened and to confirm eligibility or record reasons for screening failure, as applicable.
- Procedures conducted as part of the participant's routine clinical management (eg, blood count) and obtained before signing of ICF may be utilized for screening or baseline purposes provided the procedure met the protocol-specified criteria and were performed within the time frame defined in the SoA.
- Additional evaluations/testing may be deemed necessary by the investigator and or the Sponsor for reasons related to participant safety. In some cases, such evaluation/testing may be potentially sensitive in nature (eg, HIV, Hepatitis C), and thus local regulations may require that additional informed consent be obtained from the participant. In these cases, such evaluations/testing will be performed in accordance with those regulations.

The maximum amount of blood collected from each participant over the duration of the study will not exceed 380.5 mL (Appendix 8).

Repeat or unscheduled samples may be taken for safety reasons or for technical issues with the samples.

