8.10.1 Screening

Approximately 4 weeks prior to intervention allocation/randomization, potential participants will be evaluated to determine that they fulfill the entry requirements as set forth in Section 5.

Participants may be rescreened after consultation with the Sponsor. Rescreening should include all screening procedures listed in the SoA, including consent review. Rescreen procedures cannot be conducted the day prior to intervention allocation/randomization if there are Day -1 procedures planned per protocol.

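### Exclusion criteria 9 and 11 look back only from screening, so neither covers new events in the interval of up to about 4 weeks before dosing

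*Combined protocol and SAP*

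**What the plan says.** In Section 5.2, criterion 9 excludes a participant who "Had major surgery, donated or lost 1 unit of blood (approximately 500 mL) within 4 weeks prior to the pre-study (screening) visit". Criterion 11 excludes one who "Has participated in another investigational study within 4 weeks (or 5 half-lives, whichever is greater) prior to the pre-study (screening) visit", and adds: "The window will be derived from the date of the last visit in the previous study". Both look-back periods end at the screening visit.

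On the distance from screening to dosing, footnote b of the Schedule of Activities (Section 1.3) says "Participants will be screened within approx. 4 weeks prior to administration of study drug", and Section 8.10.1 says "Approximately 4 weeks prior to intervention allocation/randomization, potential participants will be evaluated". The Schedule of Activities lists the eligibility check at screening and again pre-dose.

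Other criteria in the same list do reach the dose. Criterion 10 bars medication "beginning approximately 2 weeks (or 5 half-lives) prior to administration of the initial dose of study drug, throughout the study". Criterion 12 (ECG) and criterion 19 (urine drug screen) each name both screening and the pre-dose time.

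**The concern.** The pre-dose eligibility check does not close the interval for these two criteria. Read again on the day of dosing, they ask the same question about the same period before screening. A participant who gave a unit of blood, had major surgery or joined another trial after screening still passes both.

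The protocol does regulate this interval for other matters. Besides criteria 10, 12 and 19, Section 5.3.3 restricts unaccustomed strenuous activity from screening up to the dose. The visible text of Section 5.3 says nothing about donating blood. This looks more like an anchoring slip than a deliberate choice.

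Two things are at stake: protection of participants who then undergo substantial blood sampling, and clean baselines for the safety laboratory tests and the viral-load series. Panels have 6 participants, and Section 6.6 allows the review before the next panel to rest on as few as 4 evaluable ones. One distorted baseline, or one participant carrying another study drug, could be 1 in 4 of the data reviewed.

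**Working it through.** **Windows.** Take the dose as day 0, screening as day -s with s at most about 28 (Section 1.3, footnote b), and 4 weeks as 28 days.

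- Criteria 9 and 11 cover day -(s + 28) to day -s. Criterion 11 reaches further back if 5 half-lives exceeds 4 weeks, but it also stops at screening.
- The interval that neither criterion covers is day -s to day 0, of length s.
- Criterion 10 covers about day -14 to day 0, for medication only. On that reading, max(0, s - 14) days have no dose-anchored exclusion for drug exposure.

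| Screening | Criteria 9 and 11 cover | Not covered by 9 or 11 | Left after criterion 10 (drug exposure only) |
|---|---|---|---|
| day -28 | day -56 to -28 | 28 days | 14 days |
| day -14 | day -42 to -14 | 14 days | 0 days |
| day -7 | day -35 to -7 | 7 days | 0 days |
| day -1 | day -29 to -1 | 1 day | 0 days |

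The last column uses the 2-week arm of criterion 10. On the 5-half-lives arm, the criterion would span all 28 days for a drug with a half-life of at least 28 / 5 = 5.6 days. Unlike criterion 11, criterion 10 does not say that the longer period governs. A blood donation involves no drug, so criterion 10 does not reach it and the third column applies in full.

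**Blood volume, as context only.** The Appendix 8 rows (collections x mL) reproduce the stated maximum:

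5 x 13 + 3 x 5 + 1 x 3 + 1 x 8.5 + 19 x 4 + 13 x 16 + 1 x 5 = 65 + 15 + 3 + 8.5 + 76 + 208 + 5 = 380.5 mL.

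Of this, the screening visit takes 13 + 5 + 3 + 16 = 37 mL, which is drawn before any event in the gap. At most 380.5 - 37 = 343.5 mL of scheduled blood could follow a 500 mL loss after screening. That is an upper figure: it includes serum pregnancy tests for women of childbearing potential only, a conditional 5 mL proviral DNA sample, and the full set of HIV RNA draws for a participant who does not start ART.

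**The case against.** The strongest reply is that the interval is not unguarded.

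- Criterion 20 requires exclusion once the investigator has any concern about participation, with no time limit, and it applies at the pre-dose check.
- Criterion 10 reaches drug exposure near the dose.
- Section 8.1.5.1 has medication from the 28 days before the dose reviewed and recorded, which should bring peri-operative or investigational drugs to light.
- Haematology, physical examination, vital signs and ECG are repeated pre-dose. Appendix 10 applies to pre-dose laboratory values and excludes a participant where the significance of an abnormal value is uncertain.
- On its plain words, criterion 11 still catches a trial already running in the 4 weeks before screening, even if it continues into the gap.

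All of this stands, and it rules out a stronger reading. A reader might infer that a participant with such an event cannot be excluded under the protocol. The documents do not support that: the gap lies in criteria 9 and 11, not in the protocol as a whole.

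A reader might also add 500 mL to the whole 380.5 mL and to the optional extra 50 mL. That is not supported either. The 37 mL taken at screening comes before the event, and Section 8.10.6 keeps the extra 50 mL within the Section 8 maximum, although note f of Appendix 8 can be read otherwise. The documents give no threshold for blood loss and study sampling combined, so none is shown to be breached.

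The safeguards still do not replace the criteria. Section 6.5 relaxes the medication rule: a participant who has not stopped all prior medications can enter, because "he/she may be included in the study if the investigator can rationalize that the specific use of a prior medication is not clinically relevant". The 28-day review records medication but does not itself exclude anyone. Appendix 10 admits a participant whose abnormal value is annotated as not clinically significant. Criterion 20 depends on the investigator learning of the event, and medical history is scheduled only at screening. A donation that leaves laboratory values unremarkable can pass all of these.

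**Conclusion.** The point holds as a narrow wording gap. Criteria 9 and 11 do not themselves cover new events between screening and dosing, a period of up to about 28 days, and the scheduled pre-dose check does not repair this. Cover is indirect and partly discretionary. It is weakest for blood donation or loss, where only criterion 20 and any abnormal pre-dose finding would act.

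The conclusion assumes that screening can fall about 4 weeks before the dose, as Sections 1.3 and 8.10.1 allow; with later screening the gap shrinks day for day. It also rests on the visible text. Most of inclusion criteria 1 to 9 and part of Section 6.5 are removed or redacted, and further cover there cannot be ruled out. The documents give no rate for such events; they are probably uncommon. No endpoint, analysis or sample-size figure changes, so the point is minor: worth correcting, but not a threat to the trial's conclusions.

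**What to change.** In criteria 9 and 11, after the reference to the screening visit, add: 'or at any time between screening and dosing'. Leave the existing look-back periods as they are; the sentence in criterion 11 on how the window is derived can stay for the look-back part. Apply both criteria in this form at the pre-dose eligibility check already in the Schedule of Activities.

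The cost is a few words in two criteria, which can go into the next amendment. No visit, test or blood draw is added. The downside is that, very rarely, a screened participant is deferred or replaced.
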